## 6.2. Recruitment and Enrolment

Recruitment and enrolment relate primarily to the initial enrolment of Local Authorities into the study. Data collection on outcomes for people rough sleeping will be captured through amended routine data collections by Local Authorities and CGL nurses/staff.

### 6.2.1. Local Authorities

In February 2024, CHI will open the Test and Learn Outreach with Health Specialism project to Local Authorities to register expressions of interest to take part in a cluster Randomised Control Trial (cRCT) to evaluate an Outreach with Health specialist service. Eligible LAs will be invited to apply. Expressions of interest from single LA areas or adjacent LAs who share both an outreach provider and are in the same integrated care system sub-region will be sought.

An online webinar will be held to introduce the Test and Learn Programme and provide more detail on the outreach with a health specialist intervention. Interested LAs will complete an online application for consideration and screening against inclusion and exclusion criteria as documented in Appendix B. Successful applicants will be notified in July 2024 and 16 Local Authority areas randomised.

The implementation partner (CGL) will work across all trial sites to 1) deliver the outreach with a health specialist intervention in sites randomised to intervention and 2) to support sites with collating and extracting routine data from their standard outreach services. CGL will appoint a team member to this routine data collection role.

### **6.2.2. Routine data relating to people rough sleeping**

Local Authorities and CGL will be guided by the evaluation team to adapt their routine data collection for the duration of the study so that data across sites is uniform and can be pooled for sharing, and to include the primary and secondary outcome measures.

Routine data will be collected via outreach workers/CGL nurses/CGL team members during service delivery and will be utilised to capture demographic characteristics and to measure baseline and follow-up housing and health outcomes, and health service usage of people living on the streets in intervention and control sites.

MHCLG will be the data controllers for this trial and all other Test and Learn trials. They will publish a privacy notice explaining what data is being collected, for what purpose, and on what legal basis. This privacy notice will explain that this routine data will be shared with Cardiff University for analysis.

Trial flow and data flow diagrams are included on the next pages (Section 6.3).

### 6.3. Flow Diagrams

Figure 1: Trial Flow Diagram

[figure not shown]

Figure 2: Quantitative Data Flow Diagram

[figure not shown]
[figure not shown]

Figure 3: Qualitative Data Flow Diagram

## 7. OUTCOME MEASURES

### 7.1. Evaluation Feasibility Criteria

As a pilot cRCT, the main outcome is evaluation feasibility criteria that will determine the viability of the trial methods, and the fidelity and acceptability of intervention delivery. The criteria were devised by the trial team, with input from expert advisors with relevant trial and subject knowledge. These were also approved by an independent Trial Steering Committee (TSC). Evaluation feasibility criteria are presented in Table 8 and will be monitored by the independent TSC.

Feasibility against these criteria will be assessed using a traffic light system (green: all criteria are met; amber: the majority of criteria are met and with adaptations to methods all criteria could be met; red: the minority of criteria are met). These criteria should be applied with discretion as during the study solutions to substantively improve each may be identified.

**Table 8: Feasibility Criterion**

Feasibility Criterion	Red	Amber	Green
Trial methods			
1. Successful recruitment and randomisation of 16 Local Authorities	<10	10-15	16
2. 12 Local Authorities remain in the pilot study	<10	10-11	≥12
3. Data is collected for more than 60% of service users at baseline and the final follow-up on primary outcome	<50%	50-60%	>60%
Intervention			
4. The intervention being delivered with fidelity	Low	Medium	High
5. The intervention is acceptable to service users, Local Authority staff, and nurses	Low	Medium	High

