## 5.2. Study Design

### 5.2.1. Two-arm pilot cluster randomised controlled trial

The study design is a two-arm pilot cluster randomised controlled trial (cRCT). Local Authorities (LAs) are the unit of randomisation. 16 eligible LAs will be randomly assigned by an independent statistician in a 1:1 ratio (8 LAs per arm) to receive funding to embed a health professional as part of the outreach team (a qualified nurse) or remain with their usual practice.

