## **8. DATA COLLECTION**

### **8.1. Data Collection Methods**

In intervention sites, housing situation data (primary outcome), health status data (secondary outcome), and health service interaction data (secondary outcome) will primarily be collected by nurses as part of their normal routine service delivery at baseline, 3 and 6 months. They will also be supported by a dedicated CGL team member and outreach workers. At follow-up, service users will either be recontacted on the streets, contacted using known telephone numbers, or nurses/CGL team member will seek to locate individuals through other service providers (e.g. hostels and day centres). CGL will amend their routine data collection platform to capture outcome data.

In control sites, housing situation data (primary outcome), health status data (secondary outcome), and health service interaction data (secondary outcome) will be collected by outreach workers as part of their normal routine service delivery at baseline. At follow-up, a dedicated CGL team member will support the collection of follow-up data at 3 and 6 months in control sites. Service users will either be recontacted on the streets, using known telephone numbers, or the CGL team member will seek to locate individuals through other service providers (e.g. hostels and day centres). The CGL team member will work across all control sites, potentially travelling between them to aid sites in collating data. They will also assist the local teams in their data uploading and in tracking service users who have previously been included as part of the study and following-up with these service users.

Data will be manually input into the CGL managed CRi Information System (CRiIS). For intervention sites, baseline data will be entered by the outreach nurse, and follow-up data with assistance from a CGL team member. For control sites, the relevant data extracts will be provided to CGL, then all data will be manually entered into CRiIS by the CGL team member.

As data will be collected by nurses and/or outreach workers ('users') as part of their everyday service delivery, there will be an element of user preference determining how it is collected. Staff can either enter data directly into the database using a CGL provided mobile device whilst they are with the service user or make paper notes and transfer them at the office via the online portal.

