**Table 9: Data Collection Procedures and Assessment Timeline**

Assessment point	Type of data	Data collection approach
First contact (four-week window to collect baseline)	Contact recording and eligibility assessment.	Nurses and outreach workers. On the street/in the community.
Baseline	Baseline characteristics (age, sex, gender, nationality, care experienced, left an institution in the last 85 days – see Appendix F), primary and secondary outcomes (pre-intervention).	Nurses and outreach workers. On the street/in the community.
Interim contact data*	Contact date for each contact occurrence with service user to record data and/or to receive treatment, care or advice.	Nurses and outreach workers and CGL team member. On the street/in the community (intervention sites only).
Midline (3 months after baseline – 4-week window to complete)	Primary and secondary outcomes including reason for non-contact if applicable.	Nurses, outreach workers, and CGL team member. On the street/in the community, telephone (if contact details provided), through other organisations (e.g. NHS).
Interim contact data*	Contact date for each contact occurrence with service user to record data and/or to receive treatment, care or advice.	Nurses and outreach workers and CGL team member. On the street/in the community (intervention sites only).
Endline (6 months after baseline – 4-week window to complete)	Primary and secondary outcomes including reason for non-contact if applicable	Nurses, outreach workers, and CGL team member. On the street/in the community, telephone (if contact details provided), through other organisations (e.g. NHS).

\*Interim contact data collected in intervention sites only to assess level of contact per service user, treatment, care or advice given (anonymised), and to facilitate follow-up data tracking

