## 9. SAMPLE SIZE AND POWER CALCULATION

### 9.1. Sample Size / Power Calculation

The aim of this pilot cRCT is to evaluate feasibility and acceptability of outreach services with a health specialism for people rough sleeping and provide indicative evidence of its effectiveness. The study will determine numbers of service users eligible for routine data collection and response rates, estimates of effect sizes and intra-cluster correlation coefficients as well as providing in-depth knowledge on the views and experiences of health outreach workers and people who received care.

A sample size calculation was provided by CHI based on the number of LAs and service users that could viably be engaged within the time and budget available. The sample size was based on 80% power, 5% alpha, a minimum detectable effect size (MDES) of 0.53, an average cluster size (LA) of 40 service users, ICC of 0.1, allocation ratio 1:1, and 10% attrition (Table 10). We therefore aim to randomise 16 clusters (LAs) with 8 to receive funding to embed a health professional as part of the outreach team (a qualified nurse) and 8 to remain with their usual practice, with a total of 711 LA service users required in total.

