### 10.2. Descriptive Statistics

A CONSORT flow diagram will show the number of LAs recruited and randomised, and withdrawals after randomisation of LAs as well as the number of service users included, and completion of baseline interview and follow-up points. The feasibility criteria relating to data collection on the primary outcome at baseline and follow-up will be reported as point estimates with 95% confidence intervals (CIs) (Campbell et al., 2012; Eldridge et al., 2016). We will also describe the number of interim contacts over the 6-month follow-up period intervention sites.

We will tabulate baseline characteristics of both the LAs (e.g. region, RSI funding allocation 2022-2025 strata) and the service user characteristics measured at baseline (e.g. age (years), sex assigned at birth, gender identity, nationality, care experienced, left an institution in the last 85 days – see Appendix F); these will be shown by trial arm and summarised using means and standard deviations (SDs) (or medians and interquartile (IQR) ranges, as appropriate) for continuous outcomes, frequencies and percentages for categorical outcomes.

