## 10.8. Missing Data

We will estimate the proportion of missing data for all covariates and outcomes. The patterning and percentage of missing data will inform the likely analytical strategy in a full-scale effectiveness trial. Using CHI guidance, if more than 5% of any variable (covariates and outcomes) is missing then we will examine whether those missing are conditional on covariates (e.g. age (years), sex, nationality, care experienced, left an institution in the last 85 days) or outcome data using logistic regression (to predict missingness). We will also use visualisation of missing data by using the R-package VIM (Templ, 2008). No imputation will be performed in this current pilot study.

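### Feasibility criterion 3 is rated on one completeness figure with no arm split, so it can be green while the control arm is below the protocol's own 50% red line

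*Protocol*

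**What the plan says.** Section 7.1 makes the feasibility criteria the main outcome of the pilot and rates them by traffic light, to be applied with discretion. Criterion 3 in Table 8 is "Data is collected for more than 60% of service users at baseline and the final follow-up on primary outcome": red below 50%, amber 50-60%, green above 60%. Neither the criterion nor its bands mention trial arm. Section 10.2 says the data-collection criteria "will be reported as point estimates with 95% confidence intervals (CIs"), and section 10.4 reports completion of the primary outcome by time point; neither mentions arm here. Elsewhere arm is named where it is wanted: section 10.2 shows baseline characteristics by arm, and section 10.4 estimates clustering by arm.

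Follow-up resources differ by arm. Under section 8.1, intervention-site data are collected mainly by the nurses at all three time points, with help from a CGL team member and outreach workers. In control sites outreach workers collect baseline data and a CGL team member supports follow-up: "The CGL team member will work across all control sites". The footnote to Table 9 adds "Interim contact data collected in intervention sites only", one stated purpose being to help track people for follow-up. Section 8.2 names payment cards for intervention nurses, while vouchers of up to £10 apply to routine data collection generally.

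On missing data, section 10.4 summarises people with valid data and section 10.8 states "No imputation will be performed in this current pilot study". The example predictors of missingness in section 10.8 do not include arm.

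**The concern.** Criterion 3 is the only numerical test in Table 8 of whether a definitive trial could measure its primary outcome, and such a trial needs that outcome in both arms. A pooled percentage lets good follow-up in nurse sites offset poor follow-up in control sites, and the protocol's own staffing makes such a gap plausible. A green rating could then sit beside a control arm that fails the same threshold.

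The second stake is the effect estimate. With no imputation, people lost to follow-up drop out of the comparison. Section 10.4 carries the estimate into the sample size of a future trial, and section 10.3 says another trial would be unnecessary if the interval showed benefit. If loss differs by arm and is related to housing, both uses are affected, and the criterion gives no warning.

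**Working it through.** **Inputs from the Protocol.** Allocation is in a "1:1 ratio (8 LAs per arm") (section 5.2.1). Section 9.1 gives "80% power, 5% alpha, a minimum detectable effect size (MDES) of 0.53" and "an average cluster size (LA) of 40 service users, ICC of 0.1, allocation ratio 1:1, and 10% attrition". That is 8 × 40 = 320 people per arm and 640 in all. The bands are those of Table 8.

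**The plan's own figure.** The design effect is 1 + (40 − 1) × 0.1 = 4.9. Using t on 14 degrees of freedom, MDES = (2.145 + 0.868) × √(2 × 4.9/320) = 3.013 × 0.175 = 0.527, which rounds to the stated 0.53. Attrition: 640/0.9 = 711. The sample size figures reproduce. The criterion 3 thresholds have no stated derivation.

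**Can green coexist with a red control arm?** With equal arms, pooled completeness = (p_I + p_C)/2.

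- 75% and 49%: 62.0%, green.
- 80% and 45%: 62.5%, green.
- 80% and 42%: 61.0%, green.
- In counts, green needs 385 of 640 (60.2%). Control at 159/320 (49.7%, red) is still green overall once intervention reaches 385 − 159 = 226/320 (70.6%).

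A gap of about 21 points is enough. If the intervention arm holds more people, less is needed. With control at 49% and an assumed split of 400 to 240, the intervention rate needed is above (0.60 × 640 − 0.49 × 240)/400 = 66.6%, against 71% with equal arms.

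**What could this do to the effect estimate?** The following are assumptions, not figures from the Protocol: no true effect; 30% housed in both arms; intervention follow-up 75% and unrelated to housing; control follow-up 49% overall. Let r be the chance that a housed control user is found, relative to one not housed. The observed control share is 0.3r/(0.3r + 0.7), and the spurious difference is 0.30 minus that.

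- r = 0.5: 0.15/0.85 = 17.6%; difference +12.4 points.
- r = 0.67: 22.3%; +7.7 points.
- r = 1: 30%; 0.
- r = 1.5: 0.45/1.15 = 39.1%; −9.1 points.
- r = 2: 0.60/1.30 = 46.2%; −16.2 points.

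**What would a per-arm rule cost?** Assume both arms truly reach 65%, 40 per LA, and an ICC of 0.1 for completeness. That ICC is borrowed from the outcome calculation and is itself an assumption. Normal approximation:

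- Pooled: SE = √(0.65 × 0.35 × 4.9/640) = 4.17 points. Chance of exceeding 60% = Φ(5/4.17) = 88%.
- Pooled plus a 50% floor in each arm: the per-arm SE is √(0.65 × 0.35 × 4.9/320) = 5.90 points, so an arm falls below 50% with probability Φ(−15/5.90) = 0.6%. The chance of green remains about 88%.
- Each arm must exceed 60%: Φ(5/5.90)² = 0.80² = 64%.

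**Precision.** Under the same clustering assumption, 75% v 49% is a gap of 26 points with 95% half-width 1.96 × √(0.0536² + 0.0619²) = 16 points.

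**The case against.** The strongest reply is that a pooled threshold is a legitimate choice, made with expert input and approved by an independent TSC that may apply it with discretion. Pooling is also inferred from silence: Table 8 does not use the word overall. The CONSORT diagram should expose the numbers, reasons for non-contact are recorded, the covariates in section 10.8 are only examples, and overall green needs every criterion to be met. Control sites are not neglected either: vouchers are intended to keep the arms equal, people are sought by telephone and through hostels and day centres, and control areas receive a £10,000 incentive (Appendix B).

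Much of this stands. Nothing in Table 8 is contradicted elsewhere, the TSC could see a gap, and criterion 3 alone does not declare the trial viable. But none of it changes how the colour is set. The discretion in section 7.1 is tied to solutions found during the study, not to imbalance between arms, and Table 8 is the decision rule itself rather than detail left to an analysis plan.

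A reader might go further and infer that the comparison is biased in favour of the intervention. The documents do not support that. Unequal completeness alone causes no bias. Bias needs follow-up to depend on housing status within an arm, and its sign reverses if housed control users are easier to find, which searching through hostels might bring about. Nor does equal completeness show that bias is absent, so a per-arm rule tests measurability in each arm, not bias.

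**Conclusion.** The point holds as a weakness in the decision rule. As written, criterion 3 can be green while the control arm is below the protocol's own 50% line. With equal arms this takes intervention follow-up of about 71% or more when control is just under 50%, and the follow-up arrangements in section 8.1 and Table 9 make a gap in that direction plausible. The rating problem is plain arithmetic and does not depend on any bias occurring.

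The consequence for the effect estimate is conditional. Under the stated assumptions it ranges from about +12 to −16 points as housed control users go from half to twice as likely to be found, passing through zero when they are equally likely. The documents settle neither sign nor size. The point is worth acting on because the remedy needs no new data, but it does not show that the trial's comparison is invalid.

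**What to change.** - **Table 8:** keep the pooled bands for criterion 3 and add that it is not rated green if completeness is below 50% in either arm.
- **Sections 10.2 and 10.4:** report completeness of the primary outcome by arm and the between-arm difference, with 95% confidence intervals that allow for clustering by LA.
- **Section 10.8:** include trial arm in the regression that predicts missingness.

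This takes a wording amendment and TSC agreement, best settled before 6-month completeness by arm is reviewed. The costs are wider intervals and almost no loss in the chance of green when both arms do well (about 88% with or without the floor at a true 65%, on the assumptions above). The floor acts on observed rates, so a control arm truly just under 50% will sometimes pass it, which is why the between-arm difference should be reported as well.

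A stricter option is to rate each arm on the full bands and let the lower arm set the colour. On the same assumptions that cuts the chance of green to about 64%. Whether that is worth it is for the TSC to decide.

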### 7.2. Primary Outcome

#### 7.2.1. Definition

The primary outcome is housing situation defined using the housing outcomes listed in the CHI adapted version of the Residential Time-Line Follow-Back (RTLFB) inventory (Tsemberis et al, 2007) (Appendix C).

At the broadest level, the inventory distinguishes between three main types of housing situation: homeless, not homeless, and living in an institution. The trial will explore changes in these housing situations. Analysis will also allow exploration of potential movement from

roofless forms of homelessness (e.g. rough sleeping) to houseless forms of homelessness (e.g. temporary accommodation).

Arguably, overall health status could also be considered a primary outcome for this intervention given the health-related support offered by the nurse. However, the ultimate objective of assertive outreach activities is to support people to stop rough sleeping and move into accommodation where their needs, including health-related needs, can be met more effectively. For this reason, the authors and MHCLG as the funder of the programme make the judgement that service users' housing status should be the primary outcome.

### **7.2.2. Instrument**

The housing outcomes listed in the RTLFB provide a point-in-time assessment on a service user's housing situation at each data collection point (baseline, midline, and endline). These housing outcomes will be added to LA routine data collection.

### **7.2.3. When is it measured?**

Housing situation will be collected at baseline, 3-month and 6-months follow-up timepoints. 6 months is the primary follow-up point, but 3 months follow-up is incorporated in case 6-month is missing.

### **7.2.4. For whom is it measured?**

The outcome measure will be collected for all service users that meet the inclusion criteria in both intervention and control sites.

### **7.2.5. Measure and validation**

The RTLFB was adapted by CHI in consultation with the UK homelessness sector to include housing outcomes that are best suited to the UK housing context.

## **7.3. Secondary Outcomes**

We will include the following secondary outcomes: health status and health service interactions. All instruments can be found in Appendices D and E.

### **7.3.1. Health status**

#### **7.3.1.1. Instrument**

LAs will adapt their routine data collection to include the 5-level EQ-5D version (EQ-5D-5L) (Appendix D). The EQ-5D-5L is a widely used generic measure of health status consisting of two parts: the EQ-5D descriptive system and the EQ visual analogue scale (EQ VAS). The EQ 5D-5L was introduced by the EuroQol Group in 2009 to improve the instrument's sensitivity and to reduce ceiling effects, as compared to the EQ-5D-3L.

The EQ-5D-5L was chosen as it is an encompassing short questionnaire, commonly used in this population, covering the domains (physical health [pain/mobility], self-care, mental health [anxiety/depression]) relevant to the study population. Consultation with LAs suggests it is of a manageable length. Furthermore, it can be converted to quality-adjusted life year (QALYS) for the economic evaluation.

